### **Assessment of Time Invariance**

#### **PREVIOUS TEXT**

To evaluate the time invariance ratio, statistical analysis of (AUC (0- $\infty$ ) Day 1) and AUC (0-  $\tau$ ) (Day14), of GSK1278863 and metabolites for each cohort will be performed separately after a log transformation of the data.

A mixed effect model will be fitted with day as fixed effects and subject as a random effect. Day 14 AUC (0-  $\tau$ ) will be compared to Day 1 AUC (0- $\infty$ ) by cohort in order to estimate the time invariance ratios,  $R_{S=}$  AUC (0-  $\tau$ , Day 14): AUC (0- $\infty$ , Day 1). The ratios will be calculated by back-transforming the difference between the LS means.

Using the pooled estimate of variance, 90% confidence intervals will be calculated for the primary comparisons, and back-transformed to the original scale.

#### **REVISED TEXT**

To evaluate the time invariance ratio, statistical analysis of (AUC (0- $\infty$ ) Day 1) and AUC (0-  $\tau$ ) (Day14), of GSK1278863 and metabolites for both the cohorts combined will be performed after a log transformation of the data.

A mixed effect model will be fitted with day as fixed effects and subject as a random effect. Day 14 AUC (0-  $\tau$ ) will be compared to Day 1 AUC (0- $\infty$ ) in order to estimate the time invariance ratios,  $R_{S=}$  AUC (0-  $\tau$ , Day 14): AUC (0- $\infty$ , Day 1). The ratios will be calculated by back-transforming the difference between the LS means.

Using the pooled estimate of variance, 90% confidence intervals will be calculated for  $R_s$ , and back-transformed to the original scale.

t _{OR tlast}	Time of last observed quantifiable concentration
t _½	Terminal phase half-life
τ	Dosing interval
t _{lag}	Lag time before observation of drug concentrations in sampled matrix
t _{max}	Time of occurrence of C _{max}

ULN	Upper limit of normal
WBC	White blood cells

Trademark Information

Trademarks of the GlaxoSmithKline group of companies
HARP

Trademarks not owned by the GlaxoSmithKline group of companies
SAS
WinNonlin

1. INTRODUCTION

The purpose of this reporting and analysis plan (RAP) is to describe the analyses to be included in the Clinical Pharmacology Study Report for Protocol 200942:

Revision Chronology: Protocol		
2013N179529_00	2014-APR-11	Original
2013N179529_01	2014-JUN-06	Amendment No. 1
2013N179529_02	2014-JUN-24	Amendment No. 2
2013N179529_03	2014-JUL-01	Amendment No. 3
2013N179529_04	2014-DEC-12	Amendment No. 4
2013N179529_05	2015-SEP-10	Amendment No. 5
2013N179529_06	2016-JUN-20	Amendment No. 6

All decisions regarding final analysis, as defined in this RAP document, have been made prior to Database Freeze (unblinding) of the study data.

2. STUDY OBJECTIVE(S) AND ENDPOINT(S)

2.1. Study Objective(s)

2.1.1. Primary Objective(s)

Objectives	Endpoints
Primary	
Characterize the steady-state PK of GSK1278863 and metabolites (GSK2391220 (M2), GSK2506104 (M3), GSK2487818 (M4), GSK2506102 (M5), GSK2531398 (M6), GSK2531401 (M13) in ESRD subjects undergoing peritoneal dialysis	
 • [AUC(0-τ), AUC (0-∞)] (Day 1 only), and Cmax of GSK1278863 and metabolites on Day 1 and Day 14
Secondary	
Evaluate the safety and tolerability of GSK1278863 in ESRD subjects undergoing peritoneal dialysis	
 • Subject incidence of treatment emergent adverse events, including clinically-significant changes in physical exams, laboratory safety tests, ECG and vital signs
Characterize the peritoneal dialysis clearance of GSK1278863 and metabolites in ESRD subjects undergoing peritoneal dialysis	
 • Peritoneal dialysis clearance, tmax and t$\frac{1}{2}$ of GSK1278863 and metabolites on Day 1 and Day 14 • Accumulation ratio and time invariance ratio (as data permit) of GSK1278863 and metabolites
Characterize the plasma profile of erythropoietin and hepcidin after repeat dose administration of GSK1278863 in ESRD subjects undergoing peritoneal dialysis	
 • Erythropoietin and hepcidin plasma concentrations
Exploratory	
Characterize the plasma protein binding of steady-state GSK1278863 and select metabolites in ESRD subjects undergoing peritoneal dialysis	
 • Steady-state GSK1278863 and metabolite unbound concentration and free fraction
Characterize the effect of different peritoneal dialysis solutions on GSK1278863 and metabolites in ESRD subjects undergoing peritoneal dialysis	
 • Descriptive summary of GSK1278863 and metabolite PK by different peritoneal dialysis solutions utilized

3. STUDY DESIGN

This is a repeat-dose, open label, 2 cohort study to assess the pharmacokinetics of GSK1278863 and metabolites in ESRD subjects undergoing peritoneal dialysis. GSK1278863 (5 mg) will be orally administered once daily for 14 days to approximately 12 ESRD subjects;

- Cohort 1 will enrol subjects on continuous ambulatory peritoneal dialysis (CAPD) to complete all dosing and critical assessments
- Cohort 2 will enrol subjects on automated peritoneal dialysis (APD) to complete all dosing and critical assessments.

Further details about the study design can be found in Section 3 of the protocol.

4. PLANNED ANALYSES

4.1. Interim Analyses

- Informal PK reviews will be conducted throughout the study to assist Phase III development of the compound

4.2. Final Analyses

The final planned analyses will be performed after all subjects have completed the study and after database freeze. See Section 8 to Section 10 for all final planned analyses for this study.

5. ANALYSIS POPULATIONS

All Screened Population

The “All Screened” population will be defined as all subjects screened.

Enrolled Population

All participants who were enrolled for the trial and for whom a record exists on the study database.

All Subjects Population

Any subject enrolled into the study who receives at least one dose of study medication will be included in the ‘All Subjects’ Population. This will be the population used for the study population and safety analyses.

Pharmacokinetic Population

The 'PK Population' is defined as subjects in the 'All Subjects' population for whom a pharmacokinetic sample was obtained and analysed. This will be the population used for the Pharmacokinetic displays.

6. HYPOTHESES AND TREATMENT COMPARISONS

Precision Estimation

This study is designed to estimate pharmacokinetic endpoints of GSK1278863 and metabolites in ESRD patients undergoing peritoneal dialysis following repeat administration of 5 mg once daily GSK1278863.

There will be two cohorts of subjects in this study: subjects with CAPD and subjects with APD.

No formal statistical hypotheses will be tested. An estimation approach will be used to evaluate the comparisons of interest, with point estimates and associated 90% confidence intervals presented to provide a range of plausible values for the comparisons.

Table 1 Treatment and Other Sub-Group Descriptions for Data Displays

Randomisation		Final Data Display (i.e. HARP / other)
Treatment	Cohort Description	Cohort
5 mg GSK1278863	Continuous Ambulatory Peritoneal Dialysis	CAPD
	Automated Peritoneal Dialysis	APD

7. GENERAL CONSIDERATIONS FOR DATA ANALYSES AND HANDLING

7.1. Reporting Conventions

- All data displays will be presented according to the Integrated Data Standards Library (IDSL) reporting standards, where applicable. In general, data will be listed by cohort, subject, and time point and summarized by cohort (i.e. by CAPD, APD and combined) and time point
- Analyses will be performed using the 9.1.3 version of the SAS System or higher (SAS is a registered trademark of the SAS Institute Inc., Cary, NC, USA). Programs will be imported into HARP and the final output will be produced by running drivers in HARP.
- Data collected at unplanned (i.e. unscheduled) time points will not be included in the summaries by visit unless otherwise stated. Unscheduled or unplanned readings will be presented in the listings and they will be included when determining worst-case flagging for post-baseline summaries.

- In all data displays, planned and actual relative times will be relative to the study drug dosing time of the relevant dosing session.
- Planned times relative to study drug dosing will be used in all summary tables and summary (mean and median) figures.
- Actual times relative to study drug will be used in all listings and individual PK figures.
- Refer to IDSL standards (when applicable) for decimal place conventions. Raw data will generally be presented to the same number of decimal places as it was collected.
- All data will be reported according to the actual treatment the subject received. Any departures from the planned treatment according to the randomization schedule will be documented in the report.
- All observations that occurred prior to dosing will be considered as part of the pre-dose period. All observations that occur during dosing will be attributed to the subject's treatment. Observations occurring after 28 days after the last dose of study medication will not be recorded in the database.
- Deviations from the analyses in the RAP will be identified in the final clinical pharmacology study report.

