### 3. STUDY DESIGN

#### 3.1. Study Design Detail

This is a repeat-dose, open label, 2 cohort study to assess the pharmacokinetics of GSK1278863 and metabolites in ESRD subjects undergoing peritoneal dialysis.

GSK1278863 (5 mg) will be orally administered once daily for 14 days to approximately 12 ESRD subjects;

- **Cohort 1** will enrol subjects on continuous ambulatory peritoneal dialysis (CAPD) to complete all dosing and critical assessments
- **Cohort 2** will enrol subjects on automated peritoneal dialysis (APD) to complete all dosing and critical assessments.

Once a total of 8 subjects across both cohorts collectively have completed the trial, enrolment will be stopped and the study will be concluded.

A sufficient number of ESRD subjects undergoing peritoneal dialysis will be enrolled in this study in order to ensure that at least 8 subjects total complete dosing and all critical assessments. However, if during an informal review of available PK data it is determined that the PK appears to be adequately characterized, the planned number of subjects may be reduced.

Blood samples for primary PK assessment will be collected on **Day 1** and **Day 14**.

To determine subject eligibility for enrolment in the study, a screening visit will be performed within 30 days of the start of dosing (prior to Day 1).

Subjects who are deemed eligible and sign the informed consent may remain in residence at the site from the afternoon of Day -1 through the last assessment on Day 17, at the discretion of the investigator or by request of the subject. Subjects will be offered to stay in residence at the study site (inpatient) or they are allowed to remain at home (outpatient) throughout the study. For subjects that choose to participate in the study as an outpatient, they will be released from the clinic and must return to the clinic for scheduled assessments.

At a minimum, study staff must ensure that subjects are in residence at the site on full PK Days (**Day 1** and **Day 14**), as well as on Days 15, and 16 for 48 and 72 h PK sampling.

All subjects are required to return to the unit 8 (+2) days from the last dose of GSK1278863 for a follow-up visit.

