## 5. STUDY TREATMENT

### 5.1. Investigational Product (GSK1278863)

	Study Treatment
Product name:	GSK1278863
Dosage form:	Tablet
Unit dose strength(s)/Dosage level(s):	5 mg/5 mg
Route/Administration/ Duration:	Oral, once daily in the morning for 14 days
Dosing instructions:	Take one tablet with approximately half a glass of water daily in the morning (Day 1 dosing time $\pm$ 1h). On Day 1 and Day14, the dose will be administered within 30 min after completion of night APD treatment or morning last fill of peritoneal dialysis fluid; on any other study days, the dose will be administered within 2 h after completion of night APD treatment or morning last fill of peritoneal dialysis fluid.
Physical description:	A round, biconvex, white film coated tablet
Manufacturer:	GlaxoSmithKline

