#### **7.1.1. Time period for collecting AE and SAE information**

AEs will be collected from the start of Study Treatment and until the follow-up contact. Medical occurrences that begin prior to the start of study treatment but after obtaining informed consent may be recorded on the Medical History/Current Medical Conditions CRF.

SAEs will be collected over the same time period as stated above for AEs. However, any SAEs assessed as related to study participation (e.g., protocol-mandated procedures, invasive tests, or change in existing therapy) or related to a GSK product will be recorded from the time a subject consents to participate in the study up to and including any follow-up contact. All SAEs will be recorded and reported to GSK within 24 h, as indicated in [Appendix 4](#).

Investigators are not obligated to actively seek AEs or SAEs in former study participants. However, if the Investigator learns of any SAE, including a death, at any time after a subject has been discharged from the study, and he/she considers the event reasonably related to the study treatment or study participation, the investigator would promptly notify GSK.

NOTE: The method of, recording, evaluating and follow-up of AEs and SAEs plus procedures for completing and transmitting SAE reports to GSK are provided in [Appendix 4](#).

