#### **Safety Follow-Up Procedures for subjects with ALT $\geq$ 3xULN:**

- Monitor subjects weekly until liver chemistries (ALT, AST, alkaline phosphatase, bilirubin) resolve, stabilize or return to within baseline values.

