## Follow-up of AEs and SAEs

After the initial AE/SAE report, the investigator is required to proactively follow each subject at subsequent visits/contacts. All AEs and SAEs will be followed until resolution, until the condition stabilizes, until the event is otherwise explained, or until the subject is lost to follow-up.

The investigator is obligated to perform or arrange for the conduct of supplemental measurements and/or evaluations as may be indicated or as requested by GSK to elucidate as fully as possible the nature and/or causality of the AE or SAE. The investigator is obligated to assist. This may include additional laboratory tests or investigations, histopathological examinations or consultation with other health care professionals. If a subject dies during participation in the study or during a recognized follow-up period, the investigator will provide GSK with a copy of any post-mortem findings, including histopathology.

New or updated information will be recorded in the originally completed data collection tool. The investigator will submit any updated SAE data to GSK within the designated reporting time frames.

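### SAP 7.1 bars recording of observations more than 28 days after the last dose, which conflicts with the protocol's follow-up of reported AEs, SAEs and liver events and with the SAP's own listing rules

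*SAP*

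**What the plan says.** **SAP 7.1, Reporting Conventions.** At the end of a bullet that sorts observations into pre-dose and treatment periods, the SAP says: "Observations occurring after 28 days after the last dose of study medication will not be recorded in the database". No exception is given there, or elsewhere in the SAP, for AE outcomes, SAE follow-up or liver events.

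**Protocol Appendix 4, Follow-up of AEs and SAEs.** "All AEs and SAEs will be followed until resolution, until the condition stabilizes, until the event is otherwise explained". Loss to follow-up is the only other end point. On where the data go: "New or updated information will be recorded in the originally completed data collection tool". Protocol Section 8 has subject data entered in eCRFs and passed to the sponsor's data system, so this is an instruction about recording as well as about care.

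**Protocol Appendix 1, Liver Safety Process.** For ALT at or above 3xULN the instruction begins "Monitor subjects weekly until liver chemistries" and runs to resolution, stabilisation or return to baseline. With a raised bilirubin or INR as well, monitoring is twice weekly to the same end point. The subject is withdrawn from the study only once safety follow-up is complete, so these tests are on-study data.

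**The SAP elsewhere.** Section 7.3 lists all available data from subjects who withdraw. Section 9.2 lists all AEs, and 9.3 lists deaths and SAEs with no time window. Section 7.5.2.1 defines a post-treatment AE with no upper limit on onset. Section 7.1 itself puts unscheduled readings in the listings and uses them in worst-case flagging.

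**The concern.** The two documents give different answers to one question: what happens to information on a reported event that arrives more than 28 days after the last dose? The protocol says to keep following the event and update the record. The SAP says the information does not enter the database.

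What is at stake is the completeness of the longest-lasting events, because only those are still open at the cut-off. AE duration in SAP 7.5.2.1 needs a resolution date. A prolonged liver event needs its later chemistries if a reader is to see whether it recovered. Safety and tolerability is a secondary objective of the study, and in a sample this small it will be judged largely from listings of individual subjects.

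**Working it through.** There is no sample-size or error-rate figure to reproduce. The check is day arithmetic and a comparison of texts.

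**Inputs**
- Dosing, Protocol 5.1: "Oral, once daily in the morning for 14 days". The last planned dose is on Day 14.
- Follow-up visit, Protocol 3.1: "All subjects are required to return to the unit 8 (+2) days from the last dose of GSK1278863 for a follow-up visit".
- Window for new AEs, Protocol 7.1.1: "AEs will be collected from the start of Study Treatment and until the follow-up contact".
- SAP cut-off: day of last dose + 28.
- Early stopping, Protocol 5.3.3: hemoglobin is checked before dosing on Days 3, 7 and 11, and a confirmed value outside the stated limits ends dosing.

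**Dates**
1. Follow-up visit: 14 + 8 = Day 22, or 14 + 10 = Day 24 with the window. Day 22 (+2) agrees with the Time and Events Table.
2. Cut-off for a completer: 14 + 28 = Day 42. That is 42 − 24 = 18 to 42 − 22 = 20 days after the follow-up visit.
3. Cut-off for a subject stopped on Day 3: 2 + 28 = Day 30 if the last dose was on Day 2, or 3 + 28 = Day 31 if it was on Day 3.

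**What the rule does not reach.** Collection of new AEs ends at Day 22 to 24, before Day 42. An event that starts on study is recorded at onset. SAP Tables 10.1 to 10.6 are summaries of AEs and SAEs (10.5 and 10.6 by subjects and occurrences), and none is titled for duration or outcome. Losing a resolution date changes no count for an on-study event.

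**What the rule does reach, taken literally**
- AE duration = resolution date − onset date + 1. For a completer, the longest duration that can be recorded is 42 − onset day + 1. For onset on Day 14 this is 29 days, and for onset on Day 22 it is 21 days. Any longer event has no resolution date and so no duration.
- Liver monitoring: 28 / 7 = 4 weekly tests at most, or 8 twice-weekly tests, fall inside the window. Later tests are absent.
- Outputs affected: the AE listings and, if a liver event occurs, conditional listings 20 to 23.

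**Setting the SAP against itself.** A repeat liver test after a stopping event is an unscheduled reading from a subject whose treatment has stopped. Sections 7.1 and 7.3 both say such data are listed. They cannot be listed if they were never recorded.

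**The case against.** Four arguments deserve an answer.

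1. **The sentence may be an onset rule.** It sits in a bullet that assigns observations to periods, so it might mean that events starting after 28 days are left out, while a resolution date only updates an existing record. This is possible. But the sentence speaks of observations and of what is recorded, and a late liver test is an observation with its own date. If a reporting window was meant, the SAP should say so.

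2. **The protocol directs the sites.** The SAP describes reporting, and SAP Section 8 already reports 5 completers, so much of the data existed when it was written. Nothing in the documents shows that a site stopped recording. This stands as a limit: the documents show a conflict in the text, and no actual loss of data.

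3. **More specific SAP text has no cap.** Sections 7.3, 7.5.2.1, 9.2 and 9.3 list events without a window. This leaves the SAP inconsistent with itself and does not settle which rule governs. One could also say that unrecorded data are not available data, but the listings would then be short with nothing to show it.

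4. **Late SAEs and pregnancy have their own routes.** This stands. A reader might infer that related SAEs arising after the cut-off are lost altogether. For "any SAE, including a death, at any time after a subject has been discharged from the study", Protocol 7.1.1 asks the investigator to notify the sponsor if the event is considered reasonably related. Appendix 4 provides a paper form or telephone once the electronic tool is off-line, and Protocol 7.2.2 uses a separate pregnancy form. The protocol does not depend on the study database for these, so the conflict is confined to follow-up of events already reported.

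**Conclusion.** The conflict holds, and it is narrow. SAP 7.1 read as written contradicts Protocol Appendices 1 and 4 and the SAP's own listing rules. It matters only for an AE, SAE or liver event that is still open after Day 42 in a completer, or after about Day 30 to 31 in a subject stopped on Day 3. For such an event the resolution date, the duration and later liver chemistries would be missing.

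The practical weight is small. SAP Section 8 gives 7 enrolled and 5 completed, and neither document reports an event open past the cut-off. One affected subject would be 1/7, about 14% of those enrolled. That is not a share of the safety population, because the number treated is not stated, and it describes a hypothetical event. A reader might also infer that SAE tables or AE incidence would be understated. For on-study events the documents do not support that, since those counts do not use outcome dates. No primary PK endpoint is involved.

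The conclusion assumes that the sentence would be applied literally, that the database it names is the one feeding the listings, and that the standard AE listing formats, which the SAP cites by code without showing, carry resolution date or duration.

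**What to change.** Either delete the sentence from SAP 7.1, or replace it with text to this effect: *New observations starting more than 28 days after the last dose are outside the reporting window. Follow-up and outcome data for AEs, SAEs and liver events that began on study, including repeat liver chemistries, are recorded up to database freeze and listed regardless of the 28-day limit.*

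Database freeze gives the rule a workable end, since SAP 4.2 places the final analyses after it. Later information continues through the sponsor's safety-reporting routes, and late related SAEs and pregnancies need no new text here.

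The cost is one SAP sentence. No analysis method, table count or data collection changes, because the protocol already requires these data.

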7.2. Data Management

Data Type	Source	Format of Data	Planned Date of Final File ¹	Responsibility
Safety	SDTM datasets	CDISC	DBF	CPDS
Biomarker	External CRO	CSV file	DBF+X ⁴ days	CPDS
SDTM PC	PK concentration data merged with SI PK	CDISC	DBF + X Days	SDTM Conversion Service (SCS)
Winnonlin file created from ADPC (PK Conc)	Analysis Dataset for PK Concentrations	CSV file	SDTM PC + X ⁴ Days	QSI (Prog)
PK Parameter	Winnonlin-posted to HARP by CPMS ³	CSV file	PK Conc Winnonlin + X ⁴ days ²	CPMS
SDTM PP	PK parameter data	CDISC	PK Parameter Winnonlin + X ⁴ days ²	SDTM Conversion Service (SCS)

1. This is for study teams to determine upfront if there is a possibility of not meeting the completion of the CPSR within 6 months of LSLV (i.e. novel data that may not be available until several months after LSLV).

2. Provided source data is clean.

3. PK concentration data is released via SMS2000 by DMPK and the SI PK dataset contains date/times and PK sample ID.

4. Standard timelines are not followed for this study.

